### 15.2 Sample Size Determination

Taking into account the quasi-experimental study design in the pilot of a comparison between pre- and post-implementation of the intervention, I based the power calculation on a recent but simple method proposed by Viechtbauer et al. suggesting a sample size of 60 as adequate. True probability is unknown, and therefore the lower bound of the probability will be considered in the context of the proposed study. Caution proposed by Kraemer is also considered, where clinical significance is the focus.

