## 2 Protocol Summary

Title:	Implementing a Skills Training Evidence-Based Treatment for Posttraumatic Stress Disorder (ISTEP)
Population:	Adult primary care patients with posttraumatic stress disorder symptoms, N=60
Intervention:	Behavioral health interventions, including web-administered and clinician administered brief Skills Training in Affective and Interpersonal Regulation (STAIR) for PTSD
Objectives:	Hybrid type 1 effectiveness-implementation trial to assess the feasibility, acceptability, and preliminary effectiveness of web-versus clinician-administered brief STAIR (primary outcome: PTSD symptoms, secondary outcome: functioning) while gathering information on implementation of both modalities. Findings will inform a full stepped-care approach to PTSD treatment that spans primary care and specialty care.
Design/Methodology:	60 patients were randomized, 30 in each condition (webSTAIR v. Brief STAIR). Participants completed study survey assessments at baseline (0 weeks), 15 weeks (active treatment), and 9-months post-randomization. To ensure consistency in timing of data collection, assessments are not linked to condition or amount of content completed.
Subject Participation Duration:	9 months

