### 5 Study Design

I-STEP is a single site, unmasked, hybrid type 1 effectiveness-implementation trial which will assess the feasibility, acceptability, and preliminary effectiveness of Brief STAIR and webSTAIR while gathering data on implementation. We will randomize 60 patients (30 in each condition). Participants will complete study survey assessments at baseline (0 weeks), 15 weeks (active treatment), and 9-months post-randomization (follow-up; see Figure 1). To ensure consistency in timing of data collection, assessments are not linked to condition or amount of content completed. We hypothesize that: 1) Brief STAIR and webSTAIR will be effective in reducing PTSD symptoms (primary effectiveness aim) and mental health symptoms (secondary effectiveness aim); 2) Brief STAIR (clinician-administered) will have advantages

over webSTAIR (self-directed) in terms of treatment completion; and 3) webSTAIR will evidence advantages over Brief STAIR in regard to scalability and sustainability. Outcomes will be assessed using survey data and chart extraction.

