**Randomization procedure:** Participants will be randomized through a randomization software. Each patient will receive a unique study ID at the time of referral to the study that is not connected to identifiable data. Before randomization, the referred patient will complete the following enrollment procedures: (1) each referred patient will complete a clinical intake at with their IBH therapist, and (for those with PTSD treatment needs) give permission for study team to contact, (2) each referred patient will complete an assessment with study staff to determine eligibility for the study, (3) each referred patient will give study staff consent to participate in the study, and (4) each referred patient will complete the baseline assessments. Once a participant gives consent to enroll in the study, they will be provided with a unique ID number and this ID number will be connected to their identifiable data (access to identifiable data will be limited). Once all four steps of enrollment (clinical intake, eligibility assessment, consent, and baseline assessment) are completed, the participant will be randomized.

**Study design schedule:** This evaluation is designed so that all patients who may benefit from PTSD treatment will be offered STAIR through in-person/telehealth format. Only those who enroll in the study are randomized to webSTAIR will have access to the webSTAIR format. Group assignment will therefore be randomized for all eligible participants. We also acknowledge that, because clinic practices cannot change overnight, after STAIR is rolled-out, some patients still may not be provided STAIR, due to their treatment preference or their therapist's preference not to complete STAIR training. Therefore, even therapists who do not complete the STAIR training will be instructed to offer STAIR as an option that may be delivered by a different IBH therapist.

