## 15 Statistical Plan

### 15.1 Study Hypotheses

Hypotheses:

- A. Brief STAIR will lead to significant change PTSD symptoms between baseline and 3 months.
- B. WebSTAIR will lead to significant change PTSD symptoms between baseline and 3 months.
- C. There will be no group differences in change in PTSD across conditions.

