### 15.3 Statistical Methods

Analyses were conducted in SPSS version 29. All continuous outcome variables were evaluated for and met the assumptions of normality (using both the Shapiro-Wilk test and the test statistics for skewness and kurtosis) and homogeneity of variance (using Levene's test; Hahs-Vaughn & Lomax, 2020). Chi-square tests and independent samples t-tests were used to examine differences in study variables between participants assigned to STAIR and webSTAIR conditions. Paired samples t-tests were used to

examine pre to post differences and pre to follow-up differences; effect sizes were calculated using Cohen's d. Participant retention, measured by percent of intervention content completed, did not meet the assumption for normality. To compare differences in engagement between STAIR and webSTAIR, we used the Kruskal-Wallis test, a non-parametric test that does not assume distributions between groups are similar. Linear mixed models with repeated measurements nested within patients were used to examine changes in study outcomes across time points and between groups. We used the restricted maximum likelihood estimator and unstructured covariance matrices for residuals. We examined fixed effects of time, treatment group, and time by treatment group interactions for all study outcomes. In post hoc analyses, we used Spearman's correlations to examine the correlation between engagement and baseline trauma symptoms of discrimination, stigma, and attitudes toward help seeking. Post hoc LMMs examined primary outcomes only (PTSD symptoms, mental health symptoms, and depression symptoms) and included two indicators of engagement, percent of assigned intervention completed and additional contact hours (count of behavioral health encounters documented in the electronic medical records).

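### The sample size of 60 is justified by a pre/post-implementation comparison, not the randomised 30 v 30 design, and the no-difference Hypothesis C is examined only by tests of difference, with no margin

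*Combined protocol and SAP*

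**What the plan says.** Section 15.2 opens its justification with "Taking into account the quasi-experimental study design in the pilot of a comparison between pre- and post-implementation of the intervention", and cites a published sample-size method as "suggesting a sample size of 60 as adequate". It continues: "True probability is unknown, and therefore the lower bound of the probability will be considered in the context of the proposed study". It does not say what event that probability describes, what value the lower bound takes, or what confidence is attached. It states no significance level, power, effect size, standard deviation, dropout allowance or margin.

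The rest of the document describes a different design. The Protocol Summary (Section 2) and Section 5 both give individual randomisation, 30 patients to each of webSTAIR and Brief STAIR. Section 12 states "Group assignment will therefore be randomized for all eligible participants".

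Section 15.1 lists three hypotheses. A and B each predict a within-arm change in PTSD symptoms from baseline. C is a between-arm statement: "There will be no group differences in change in PTSD across conditions".

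For comparing the arms on PTSD change, Section 15.3 offers two tools. One is described as "Chi-square tests and independent samples t-tests were used to examine differences in study variables between participants assigned to STAIR and webSTAIR conditions" (of these, the t-test is the one that applies to PCL-5 scores). The other is a linear mixed model with time, group and time-by-group effects. Both test for a difference.

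**The concern.** There are two linked problems. First, the sample-size rationale is written for a non-randomised comparison of periods before and after implementation. A reader who wants to know what 30 v 30 can deliver on the between-arm question finds nothing in 15.2 that answers it, yet the section says the number is adequate.

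Second, C predicts the absence of a difference, and the listed procedures can only fail to find one. A non-significant result becomes more likely as the sample shrinks or dropout rises. If non-significance is taken as support, the hypothesis is easiest to confirm when the data say least.

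The similarity reading is a realistic risk. Section 3.2 already reports comparable effect sizes for the two delivery modes. Section 5 expects webSTAIR to do better on scalability and sustainability, although it also expects Brief STAIR to do better on completion. Section 2 says the findings will inform a stepped-care approach. A null interaction read as equal effectiveness could tilt that model towards webSTAIR without evidence that the clinical results are close.

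**Working it through.** **Can 60 be reproduced?** No. Section 15.2 supplies none of the inputs that a between-arm calculation would need, so there is no stated calculation to check.

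**What 30 per arm gives.** From the documents: n = 30 per arm (Sections 2 and 5) and a PCL-5 range of 0 to 80 (Section 4.2.1). Assumed, because the documents are silent: two-sided 5%, a t-test approximation at one timepoint, no dropout, independent patients, and results in units of the SD of the PCL-5 change score.

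*Within an arm (Hypotheses A and B), 95% CI half-width:*

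t(0.975, 29) / √30 = 2.045 / 5.477 = **0.37 SD**

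*Between arms (Hypothesis C), 95% CI half-width:*

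t(0.975, 58) × √(2/30) = 2.002 × 0.2582 = **0.52 SD**

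In PCL-5 points, for an assumed range of change-score SDs:

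| SD of change (assumed) | Between-arm 95% half-width |
|---|---|
| 10 | 0.517 × 10 = 5.2 points |
| 15 | 0.517 × 15 = 7.8 points |
| 20 | 0.517 × 20 = 10.3 points |

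*Effect of dropout.* With an assumed 20% loss (24 per arm), the between-arm half-width is 2.013 × √(2/24) = 0.58 SD.

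*How often would a real difference go unnoticed?* If the true difference were 0.5 SD, a two-sided 5% t-test with 30 per arm has about 48% power (noncentral t, noncentrality 0.5 / 0.2582 = 1.94). A non-significant result would occur about half the time.

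*Could C be shown formally at this size?* An equivalence test at 5% per side needs the 90% CI to lie inside the margin. Its half-width is t(0.95, 58) × √(2/30) = 1.672 × 0.2582 = 0.43 SD. Suppose the arms truly do not differ, and take an illustrative margin of 0.5 SD. The probability of success, integrated over the chi-square distribution of the pooled variance, is **0.21**; a simulation of 200,000 trials gave 0.215. The margin at which the probability reaches 80% is about **0.76 SD**, or 7.6, 11.5 and 15.3 points for SDs of 10, 15 and 20.

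**The case against.** The strongest reply is that a pre/post basis is not foreign to this trial. The pilot in 15.2 may mean this study, whose effectiveness aim is called preliminary. Two of its three hypotheses are within-arm pre/post contrasts, with paired t-tests planned. That has force for A and B: their basis is undocumented, but 60 is not shown to be too small for them. It does not rescue the quasi-experimental label, which conflicts with Sections 5 and 12, and it gives no basis for C.

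It can also be said that 15.2 rests on cited references that do not appear in Section 17, so the method cannot be judged from the document. That is right, and this point makes no claim about what the method covers. It says only that the inputs and their link to C are not shown.

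Next, C appears only in 15.1; the hypotheses in Sections 4.1 and 5 do not repeat it, and nowhere does the plan say that a non-significant term will confirm it. That is true, and the stepped-care consequence is a risk rather than a stated intention. But C is a formal hypothesis in the statistical section, and difference tests are the only between-arm procedures given for it.

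Finally, the margins and SDs used for illustration are assumed, and the half-width ignores possible clustering by the 10 study therapists as well as dropout. Those omissions make 0.52 SD a best case. In the other direction, baseline information in the mixed model could narrow the interval somewhat, which is a reason to report the model's own interval.

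**Conclusion.** The concern holds on both counts. The justification in 15.2 describes a design other than the randomised trial, and C cannot be supported by the analyses listed. Under the stated assumptions, the between-arm difference is known only to within about 0.52 SD either way, or roughly 5 to 10 PCL-5 points if the change-score SD lies between 10 and 20. An equivalence claim would have a reasonable chance of success only with a margin near three-quarters of an SD. The textual conflict and the missing margin are certain; the point values depend on an SD that the documents do not give. This should be corrected, but it does not call into question the size of the trial for its preliminary aims or for Hypotheses A and B.

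**What to change.** In 15.2, keep the existing basis on record and add text along these lines:

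> This basis was a pre/post-implementation comparison and does not match the randomised 30 v 30 design. The sample of 60 was not sized for Hypothesis C. Approximate precision with 30 per arm, calculated afterwards (two-sided 5%, t-test approximation at one timepoint, independent patients, no dropout, in SDs of the PCL-5 change score): 95% CI half-width about 0.37 SD within an arm and about 0.52 SD between arms.

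If a calculation for C does exist, give it with its inputs in place of the second sentence.

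In 15.1 and 15.3, report C as the estimated between-arm difference in PCL-5 change with its 95% CI from the mixed model, using the observed data and actual dropout. State that similarity will not be concluded from a non-significant time-by-group term.

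Do not add an equivalence margin now. Section 15.3 is written as if the analyses are complete, so a margin would be post hoc. More patients are not proposed; Section 14.1 records only 30 webSTAIR accounts.

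The cost is a few sentences and one reported interval from a model already fitted. The price is a less favourable account of what 60 patients deliver, and C can no longer be reported as confirmed.

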### 15.3 Statistical Methods

Analyses were conducted in SPSS version 29. All continuous outcome variables were evaluated for and met the assumptions of normality (using both the Shapiro-Wilk test and the test statistics for skewness and kurtosis) and homogeneity of variance (using Levene's test; Hahs-Vaughn & Lomax, 2020). Chi-square tests and independent samples t-tests were used to examine differences in study variables between participants assigned to STAIR and webSTAIR conditions. Paired samples t-tests were used to

examine pre to post differences and pre to follow-up differences; effect sizes were calculated using Cohen's d. Participant retention, measured by percent of intervention content completed, did not meet the assumption for normality. To compare differences in engagement between STAIR and webSTAIR, we used the Kruskal-Wallis test, a non-parametric test that does not assume distributions between groups are similar. Linear mixed models with repeated measurements nested within patients were used to examine changes in study outcomes across time points and between groups. We used the restricted maximum likelihood estimator and unstructured covariance matrices for residuals. We examined fixed effects of time, treatment group, and time by treatment group interactions for all study outcomes. In post hoc analyses, we used Spearman's correlations to examine the correlation between engagement and baseline trauma symptoms of discrimination, stigma, and attitudes toward help seeking. Post hoc LMMs examined primary outcomes only (PTSD symptoms, mental health symptoms, and depression symptoms) and included two indicators of engagement, percent of assigned intervention completed and additional contact hours (count of behavioral health encounters documented in the electronic medical records).

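### Within-arm change is tested by paired t-tests that use only observed pairs, although the planned mixed model can estimate the same changes from all observed scores

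*Combined protocol and SAP*

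**What the plan says.** Section 15.3 (Statistical Methods) describes two analyses of change over time.

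- Paired tests: "Paired samples t-tests were used to" "examine pre to post differences and pre to follow-up differences; effect sizes were calculated using" Cohen's d.
- A mixed model: "Linear mixed models with repeated measurements nested within patients were used to examine changes in study outcomes across time points and between groups". On estimation: "We used the restricted maximum likelihood estimator and unstructured covariance matrices for residuals". On terms: "We examined fixed effects of time, treatment group, and time by treatment group interactions for all study outcomes".

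Three other sections bear on the point. Section 5 plans 60 patients, 30 per arm, seen at baseline, 15 weeks and 9 months, and says that "assessments are not linked to condition or amount of content completed". Section 12 (Randomization procedure) places the baseline assessment before randomization. Hypotheses A and B in section 15.1 are changes in PTSD symptoms within each format from baseline to 3 months; the nearest scheduled visit is at 15 weeks.

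The documents do not say:

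- which of the two analyses decides hypotheses A and B;
- whether the paired tests are run within arm or pooled;
- how missing assessments are handled;
- whether time in the model is categorical or linear;
- which standard deviation divides d.

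No assessment dropout rate is given. Retention in section 4.2.1 is the share of intervention content completed, which is a different quantity.

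**The concern.** A paired t-test needs both scores. Anyone without the 15-week score leaves the 15-week change, its p-value and its d, and the same holds at 9 months. The design intends to assess people however much of the intervention they finish, so leaving out observed baseline scores (and 15-week scores for the 9-month change) sits badly with it.

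A likelihood-based model with unstructured covariance keeps those scores. Under missing-at-random loss it corrects the estimated change for the part of the loss that earlier scores explain. The plan therefore holds two answers to one question, does not rank them, and ties the effect size to the paired test. At stake are the within-arm estimates for the primary effectiveness aim, which section 2 says will inform a later stepped-care approach.

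**Working it through.** **Plan's own figure.** There is none to reproduce. The documents give no dropout rate, standard deviation or correlation for the PCL-5. The sample size of 60 is not in dispute here. All settings below are assumptions.

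**1. Can the model give the same contrasts?** On a simulated complete data set, a REML model with categorical time by group gave within-arm changes of −8.898 and −9.048, identical to the paired means. With time linear it gave −3.17 and −8.23. This check used a random-intercept model. The contrasts agree only if time is categorical, and they have to be requested, because the plan mentions only the fixed effects.

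**2. Large-sample bias at 9 months.** Assumed: 400,000 patients; SDs 12, 17 and 17 at baseline, 15 weeks and 9 months; correlations 0.5 (baseline with 15 weeks), 0.4 (baseline with 9 months) and 0.6 (15 weeks with 9 months); true change −10; 30% missing at 9 months. Loss is logistic in one earlier score, and higher scorers are lost more often.

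| Log-odds of loss per point | Paired mean, loss follows 15-week score | Paired mean, loss follows baseline score |
|---|---|---|
| 0.03 | −10.62 | about −9.5 |
| 0.05 | −10.95 | about −9.2 |
| 0.08 | −11.28 | about −8.7 |

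The likelihood estimate was near −10.0 in every row of both columns. The extremes are errors of (11.28 − 10)/10 = 13% in one direction and (10 − 8.7)/10 = 13% in the other.

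**3. One arm of 30, both visits.** Assumed: SD 14 throughout; baseline correlation 0.4; 20% missing at 15 weeks and 30% at 9 months, leaving on average 24 and 21 pairs; true change −10 at both; loss depends on the last observed score with log-odds 0.5 per SD; 1,500 runs.

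| Who is lost | Paired, 15 weeks | Likelihood, 15 weeks | Paired, 9 months | Likelihood, 9 months |
|---|---|---|---|---|
| Higher scorers | −9.27 | −10.04 | −9.39 | −10.06 |
| Lower scorers | −10.83 | −10.02 | −10.77 | −10.05 |
| Unrelated to score | −10.05 | −10.02 | −10.10 | −10.05 |

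The 15-week contrast, which serves hypotheses A and B, is therefore exposed too. Over all settings run (10–30% missing at 15 weeks, 20–40% at 9 months, correlations 0.4 and 0.6, log-odds from −0.5 to 1.0 per SD), paired means ran from −7.91 to −11.25 and likelihood estimates from −10.00 to −10.16.

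**4. Precision when loss is unrelated to scores.** In the last row above, the 9-month standard error is 3.25 paired and 3.12 by likelihood: 1 − 3.12/3.25 = 4% smaller. Neither method is biased.

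**5. Denominator of d.** With equal SDs, d on the SD of change equals d on the baseline SD times 1/√(2(1 − r)). The multiplier is 0.85, 1.00, 1.29 and 1.58 at r = 0.3, 0.5, 0.7 and 0.8. With the unequal SDs of step 2 and r = 0.4, the SD of change is √(12² + 17² − 2 × 0.4 × 12 × 17) = √269.8 = 16.4. A change of 10 is then d = 10/16.4 = 0.61 on that SD and 10/12 = 0.83 on the baseline SD. The choice alone moves d, with no dropout at all, and either denominator can be the larger.

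**The case against.** The strongest reply is that analysis of all observed data is not absent: the mixed model is planned for every outcome, assessments do not depend on content completed, and section 9.1.2 describes several contact methods and incentives to keep people in. The trial calls its effectiveness aim preliminary, no dropout rate is given, and the paired tests may be only descriptive. This stands in part. It means that the remedy is a ranking of two analyses and a contrast request, not a new method. It does not remove the problem, because the plan attaches the effect size to the paired test and leaves open which analysis governs.

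Three stronger readings are tempting, and the documents do not support them.

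- *The paired effects are too favourable.* This holds if loss follows the 15-week score, but reverses under the same settings if loss follows the baseline score. Nothing in the documents says which mechanism applies.
- *The plan already reports the same contrasts from the model.* It states neither categorical time nor within-arm contrasts.
- *The baseline SD is the right denominator and would bring d down.* That choice is a preference. In step 5 it raises d from 0.61 to 0.83. The missing denominator is an omission of detail. Whether the resulting d is comparable with earlier trials depends on how those trials computed theirs, which the documents do not show.

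**Conclusion.** The point holds as a cheap improvement to the analysis of change. The paired t-tests discard observed scores that the planned model would use. If loss depends on earlier scores, the paired change and its d are biased, with a sign that cannot be known in advance. At an assumed 30% loss and a true 9-month change of −10, the large-sample error is up to about 13% either way. If loss is unrelated to scores, the cost is a few percent in standard error; with complete follow-up it is nil.

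The conclusion rests on loss being missing at random given observed scores, and on time being categorical. If loss depends on unobserved scores, the mixed model is not protected either. The assumed SDs, correlations and loss rates are illustrations, not estimates for this trial.

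**What to change.** In section 15.3:

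1. Name the mixed-model within-arm contrasts, baseline to 15 weeks and baseline to 9 months, with 95% CIs, as the analysis of change. State that the 15-week contrast decides hypotheses A and B, and that time is categorical.
2. Drop the paired t-tests, or label them supplementary analyses of observed pairs and give the number of pairs per arm and visit.
3. Compute d from the model-estimated change, state its denominator, and use the same one for all outcomes, arms and visits.

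A sensitivity run that assumes missing scores are worse by fixed steps would probe the missing-at-random assumption. It is optional and would be new analysis.

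Section 15.3 is written in the past tense, so the cost is a change of wording, one contrast request on a model already fitted, and recalculation of d. Reported effects may move in either direction.

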## 8 Study Intervention

### *Clinician-administered Brief STAIR*

Participants randomized to Brief STAIR complete five 30-minute sessions with a study therapist via telemedicine or in-person based on patient preference and Covid-19 restrictions in the setting. Brief STAIR is five sessions and includes all core elements of traditional 10-session STAIR. Each session begins with review of the patients' most recent PCL-5 score (documented in the medical record by the RA). Session 1 provides psychoeducation around the impact of trauma on emotions and relationships, an introduction to the treatment program structure, and a focused breathing exercise. Sessions 2-4 focus on emotion regulation skills across the body, thought, and behavior channels (i.e., the cognitive behavioral therapy triad). These include emotion regulation techniques such as focused breathing and emotion surfing to down-regulate symptoms of over-activation (e.g., anxiety, hyperarousal) and techniques such as behavioral activation and pleasurable activities planning to up-regulate individuals when they are in a depressive or dysthymic state. Session 5 focuses on compassion, strategies for improving social engagement and sustaining relationships (e.g., conflict resolution), review of treatment progress, and a plan to continue use of skills.

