### *Web-administered STAIR (webSTAIR)*

Participants randomized to webSTAIR complete the program at their own pace. WebSTAIR includes the same content as Brief STAIR in ten online modules, which include audio, video, and text delivery of psychoeducation and therapy components, with interactive exercises to assist in skills practice. All webSTAIR participants will have a therapist on record for treatment oversight (in case higher-level of care is needed) and for treatment planning purposes. In some cases, webSTAIR participants will have access to their study therapists for sessions outside of this treatment, i.e., support that is not PTSD-specific. This may include regular therapy sessions (which typically occur every 4-6 weeks in usual care), but *not* Brief STAIR or other trauma-focused therapies during the treatment window. The RA provides patients with unique login information, technology support, and lightly encourages engagement through biweekly reminder phone calls/texts. The principal investigator (PI) and RA have access to administrator-level login, which allows them to access behavioral data on participant progress (time spent, modules completed). To protect patient privacy, open text fields within webSTAIR (e.g., personal written answers to exercises and modules) are not viewable by study staff. Patients have access to the program for all 9 months of study participation, though progress is only reported back to study therapists during the active treatment phase (weeks 0-15).

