### *Study Therapists: Training, Fidelity, and Supervision*

Study therapists (N=10) are behavioral health specialists in integrated primary care, including Master's-level social workers and doctorate-level psychologists. The PI, a nationally certified trainer in Brief STAIR, leads a 4-hour didactic training available to all therapists. Study therapists receive the Brief STAIR manual developed by Drs. [name], [name], & [name], and tailored to the local setting by the PI and CAB. Post-training, the study team sends a follow-up email to determine interest in research participation. Therapist participation in the study is voluntary. To account for therapist turnover and maximize uptake in usual care, trainings are ongoing as new hires and trainees join the clinic. During the trial, the PI provides ongoing supervision to study therapists through biweekly group consultation and individual written feedback on each session of the first two training cases. Consultation includes case review and discussion of real-time barriers/facilitators to implementation. All Brief STAIR sessions are audio-recorded to allow for fidelity assessment. Fidelity checklists (developed by [name] and adapted for our version of the manual) assess adherence, defined as completion of all session components (0 = not implemented, 1 = implemented, N/A = unable to complete), and competency, defined as how skillfully each component was delivered from 0 (not completed) to 7 (excellent). Average adherence and competency scores are calculated for each session. Fidelity monitoring for the purposes of training (written feedback on two training cases) will happen in real-time. Overall fidelity will be calculated at study completion based on 20% of Brief STAIR sessions selected at random. Fidelity will be assessed by two raters.

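### Section 15.3 treats patients as independent although a pool of 10 therapists treats the 30 Brief STAIR patients; if the therapist ICC is positive, the Brief STAIR change is reported too precisely, while the direction for the arm contrast is uncertain

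*Combined protocol and SAP*

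**What the plan says.** Section 5 allocates 60 patients equally, 30 to Brief STAIR and 30 to webSTAIR. Section 8 states "Participants randomized to Brief STAIR complete five 30-minute sessions with a study therapist". On the therapists it says "Study therapists (N=10) are behavioral health specialists in integrated primary care", a group that includes both social workers and psychologists. The pool is not fixed: "To account for therapist turnover and maximize uptake in usual care, trainings are ongoing as new hires and trainees join the clinic".

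The webSTAIR arm is self-paced, but not without therapists. Section 8 says "All webSTAIR participants will have a therapist on record for treatment oversight", and adds "In some cases, webSTAIR participants will have access to their study therapists for sessions outside of this treatment".

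Section 15.3 lists chi-square tests, independent and paired t-tests, a Kruskal-Wallis test for retention, Spearman correlations and mixed models. On the mixed models it says "Linear mixed models with repeated measurements nested within patients were used to examine changes in study outcomes across time points and between groups", with fixed effects of time, group and their interaction. Sections 15.1 to 15.3 contain no therapist effect, cluster-robust variance, ICC or therapist sensitivity analysis. The randomization text in Section 12 does not mention stratifying by therapist.

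**The concern.** Patients treated by the same clinician tend to have more similar outcomes than patients of different clinicians. The protocol itself allows for variation in delivery: it scores sessions for adherence and competency, and gives therapists written feedback on their first two training cases. Yet the analysis counts the 30 Brief STAIR patients as 30 independent pieces of information.

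Hypothesis A in Section 15.1 is most exposed. It claims a significant change within Brief STAIR, and an understated standard error makes that claim easier to reach. Hypothesis C, no group difference in change, depends on the time-by-group contrast. Its standard error may also be wrong, but there the direction depends on where the therapist effects act.

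**Working it through.** **The plan's own figure.** Section 15.2 gives a total of 60 but no alpha, power, effect size, standard deviation or ICC. It cannot be reproduced from the text, and nothing in it allows for clustering.

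**Inputs from the documents.** 30 Brief STAIR and 30 webSTAIR patients (Section 5); 10 study therapists (Section 8).

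**Assumptions.** ICC of change scores by therapist: 0.01 to 0.20. Test level: two-sided 5%. Caseload: 30/10 = 3 as the base case. As an illustration of unevenness, caseloads of 10, 6, 4, 3, 2, 1, 1, 1, 1, 1, for which the size-weighted mean caseload is m* = (100+36+16+9+4+5)/30 = 170/30 = 5.67.

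**Formulas.**
- Design effect: DE = 1 + (m* − 1) × ICC.
- Brief STAIR change: true SE / reported SE = √DE.
- Arm contrast, clustering in Brief STAIR only and equal variances: ratio = √((DE + 1)/2).
- Actual level of a nominal 5% test: 2 × P(t > t_crit / ratio), with 29 df within the arm (t_crit 2.045) and 58 df between arms (t_crit 2.002).

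Example, ICC 0.10 and m* = 3: DE = 1 + 2 × 0.10 = 1.20. The within-arm ratio is √1.20 = 1.095 and the contrast ratio is √(2.20/2) = 1.049. The effective sample size is 30/1.20 = 25.0.

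| Caseload | ICC | DE | SE ratio, Brief STAIR | Level, Brief STAIR | SE ratio, contrast | Level, contrast |
|---|---|---|---|---|---|---|
| 10 × 3 | 0.01 | 1.02 | 1.010 | 5.2% | 1.005 | 5.1% |
| 10 × 3 | 0.05 | 1.10 | 1.049 | 6.1% | 1.025 | 5.6% |
| 10 × 3 | 0.10 | 1.20 | 1.095 | 7.2% | 1.049 | 6.1% |
| 10 × 3 | 0.20 | 1.40 | 1.183 | 9.5% | 1.095 | 7.3% |
| Uneven | 0.01 | 1.05 | 1.023 | 5.5% | 1.012 | 5.3% |
| Uneven | 0.05 | 1.23 | 1.111 | 7.6% | 1.057 | 6.3% |
| Uneven | 0.10 | 1.47 | 1.211 | 10.2% | 1.111 | 7.7% |
| Uneven | 0.20 | 1.93 | 1.390 | 15.2% | 1.211 | 10.4% |

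The contrast columns hold only if clustering is confined to Brief STAIR.

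**Check by simulation** (60,000 replicates, t-tests on change, ICC 0.05, 0.10, 0.20). With 10 × 3, the level is 6.1%, 7.3%, 9.8% for Brief STAIR and 5.4%, 6.2%, 7.4% for the contrast. With the uneven caseload it is 7.8%, 10.4%, 15.6% and 6.4%, 7.8%, 10.8%. At ICC 0 all are about 5%.

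**The other possibility for the contrast.** Suppose each therapist has the same effect on change in both arms, with matching caseloads of 3. The effect then cancels from the difference, and true SE / reported SE is about √(1 − ICC) = 0.975, 0.949, 0.894 at ICC 0.05, 0.10, 0.20. The simulated level is 4.4%, 4.0%, 3.1%, so the planned test would be conservative.

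**The case against.** The strongest objection concerns the arm contrast. A reader might infer that clustering exists in one arm only, so that the standard error of the contrast is certainly too small and Brief STAIR looks more precisely estimated than webSTAIR. The documents do not support this. Every webSTAIR patient has a therapist on record and some see a study therapist for other sessions (Section 8). Clinicians can follow webSTAIR progress on a dashboard, and patients may change from webSTAIR to the clinician-led format (Section 12). Full sharing of therapist effects is an extreme case, and effects mainly in Brief STAIR are more natural for a self-paced comparator, but the direction is not settled. This part of the objection stands.

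A second objection is that neither the ICC nor the caseloads are given. This also stands. The average of 3 is arithmetic, not a documented caseload. Therapists turn over, not all ten need have delivered Brief STAIR, and outpatient psychiatry therapists may be added (Section 12). At ICC 0.01 and 3 patients each, the shortfall is only 1% for Brief STAIR and 0.5% for the contrast.

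Third, this is a 60-patient trial of feasibility and preliminary effectiveness, and an understated contrast standard error raises the chance of a false difference. It therefore works against hypothesis C, not for it. That is correct, and leaves hypothesis A as the clear exposure.

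Finally, about ten therapists will estimate a variance component poorly. This is a reason to add a sensitivity range, not to leave therapist out.

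**Conclusion.** The point holds conditionally. No planned analysis accounts for therapist, and for any positive therapist ICC with shared caseloads the standard error and p-value for the Brief STAIR change are too optimistic. The effect is modest at equal caseloads over plausible low ICCs and grows when a few therapists carry most patients; in the uneven example, the nominal 5% test reaches about 10% at ICC 0.10. These sizes rest on the assumed ICCs, caseloads and 5% level.

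For the arm contrast, the documents establish only that the standard error may be wrong. It is too small if therapist effects act mainly in Brief STAIR and possibly too large if they are shared. This is a worthwhile correction to the error bars. It does not show that the trial's conclusions are wrong.

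**What to change.** 1. Record the treating therapist for each Brief STAIR patient and the on-record therapist for each webSTAIR patient, and report the caseloads.
2. In Section 15.3, add a random therapist effect on post-baseline change for Brief STAIR patients (a partially nested model), with Satterthwaite or Kenward-Roger degrees of freedom. Take the within-arm Brief STAIR change from this model, not from the paired t-test.
3. Also report the Brief STAIR and between-arm intervals over a range of ICCs, for example 0.01 to 0.20, using the observed caseloads. This covers a variance estimate of zero or a model that fails to converge.
4. Add a sensitivity model in which the on-record therapist acts in both arms, since the main model assumes that webSTAIR patients are unclustered.

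Cost: slightly wider Brief STAIR intervals, one model term, a short table and one variable to link. Therapist identity is not on the chart extraction list in Sections 4.2 and 12. The study team can probably retrieve it from session records, but that is an inference. Section 15.3 is written in the past tense, so some reanalysis is likely to be needed as well as new wording.
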